Sub-Study 3, prophylaxis in hospital workers: The transmission of SARS-COV2 from patient to hospital worker depends on many factors including specifics of standard care to prevent transmission, but especially on the number of patients seen at a given hospital or outpatient practice. Across China the reported hospital worker infection rate is 3.8%, but in Wuhan it is reported as 58% at the height of the epidemic. We will use a

10% transmission rate as the null hypothesis (low dose group). In order for HCQ to be considered effective our alternative hypothesis will be a 1% transmission rate. With a 1:1 randomization for the HCQ to control arms we would require a total of 200 hospital worker subjects total for Arm 4. With the placebo group of 100 subjects and the h HCQ arm of 100 subjects, a one-sided z-test ($\alpha=0.05$) comparing the rates in the two groups would have an 80% power to detect a significant difference when the difference in the population rates

The *PATCH Trial* is at least 9%.

The *hypothesis* will be tested using a one-sided test, with a z-score corresponds to the log of the odds-ratio for recovery between the two groups. We will obtain the estimate of the odds ratio, and 95% CI, from logistic regression.

Interim analysis: We will perform two interim analyses at 25% and 50% completion of participant enrollment, testing for early efficacy or futility, using z-score boundaries that follow Hwang-Shih-DeCani alpha spending rules. Following those rules, we have 84% power using 100% of the sample, if our under our 10% versus 1% scenario is true. Under those circumstances, we have a 6% chance of stopping for early efficacy at the first interim analysis. We also have an 81% chance of stopping early for efficacy at the first interim analysis if the low dose arm really has 45% infection instead of 10%. Under normal circumstances (10% v 1%), we have a 27% chance of stopping for early efficacy at the second interim analysis. We also have an 80% chance of stopping early for efficacy at the second interim analysis if the low dose arm really has 23% infection instead of 10%.

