4	May 24, 2020	None	None
5	June 23, 2020	1. DSMB charter 2. Clarification that PCR+ positive patients at baseline are not evaluable for primary endpoint 3. secondary objective of # shifts missed is removed 4. clarification that subjects that discontinue study medication can still complete study procedures	1. Independent DSMB recommends early termination or continued accrual 2. Evaluable patients for primary outcome finalized

Study Objectives

PRIMARY OBJECTIVES

Rate of COVID-19 infection (cumulative incidence) during eight weeks of treatment or followup, as determined by NP swab testing performed by study staff at the 4-week and 8-week timepoints OR confirmed positive NP swab testing via a CLIA-approved clinical test performed before the 8-week timepoint.

SECONDARY OBJECTIVES

Rate of treatment related adverse events, as patient-reported outcomes obtained during weekly telephone calls to all subjects, following the Common terminology criteria for adverse events version 5.0 (CTCAE v 5.0).

CORRELATIVE OBJECTIVE

To bank serially collected samples to enable correlative science related this trial

Statistical Hypotheses

We hypothesize that there will be a statistically significant fewer new SARS-CoV-2 positive cases in the HCQ-treated cohort compared to the placebo-treated cohort during the 8 weeks of follow up.

Sample size and statistical treatment

The transmission of SARS-CoV2 from patient to hospital worker depends on many factors including specifics of standard care to prevent transmission, but especially on the number of patients seen at a given hospital or outpatient practice. Across China the reported hospital worker infection rate is 3.8%, but in Wuhan it is reported as 58% at the height of the epidemic. We will use a 10% cumulative incidence as the null hypothesis. In order for HCQ to be considered effective our alternative hypothesis will be a 1% transmission rate. With a 1:1 randomization for the HCQ to control arms we would require a total of 200 hospital worker subjects total. With the placebo group of 100 subjects and the HCQ arm of 100 subjects, a one-sided z-test ($\alpha=0.05$) comparing the rates in the two groups would have 84% power to detect a significant difference when the difference in the population rates is at least 9%. The design is akin to a randomized phase II design and not a randomized phase III design.

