The hypothesis will be tested using a one-sided test, with a z-score corresponds to the log of the odds-ratio for remaining uninfected between the two groups. We will obtain the estimate of the odds ratio, and 95% CI, from logistic regression.

Randomization process

The study is a randomized, double-blind controlled trial. Randomization will be conducted via the Penn Investigational Drug Service, following a block randomization strategy. Fixed blocks of 8 will be assigned using well-established proprietary software for clinical trials (Sealed Envelope, London UK). Randomization will be kept confidential at the IDS until the pre-specified interim and final analyses. If any SAEs occur or if subjects become SARS-CoV-2 positive, those subjects can be unblinded by written request of the PIs to the IDS team.

General

Statistical analyses will be performed using Stata v16, SAS ® software v9.4 or later, or R. All statistical analyses will mirror those of the treatment groups of Hydroxychloroquine (HCQ) and Placebo.

Without any other specification, all statistical tests will be conducted with a two-sided 5% error. The primary hypothesis will also be tested with a 5% type-one error, but that error will be one sided, corresponding to the nature of the interim analyses. Small portions of the type 1 and type 2 error will be spent on interim

analyses, following Hwang-Shih-DeCani alpha and beta spending rules, leaving error rates at the final analysis slightly reduced.

Prior to analysis, data will be screened, cleaned, and examined for outliers using standard methods. Demographic and outcome variables will be summarized overall and by treatment. Continuous measurements will be described by means \pm standard deviations or medians with minimum and maximum or the interquartile range (IQR). Binary outcomes will be described by frequencies and proportions (percentages).

The results of randomization will be examined by comparing treatment arms for demographic and other relevant variables, to test for incidental bias. We will use two-sample statistics (t-tests or Wilcoxon tests) or contingency table methods (chi-square or Fisher's exact tests) as appropriate.

Primary Analysis

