The primary analysis will consist of a z-test, corresponding to the log of the odds-ratio for the proportion well in the HCQ group, versus the proportion well in the placebo group at the end of 8 weeks. The estimate will be made using either logistic regression or directly using contingency table methods. Tests will be one-sided, with type one error based on the alpha spending plan, with an overall type one error of 5%.

Interim Analysis

We will perform two interim analyses at 25% and 50% completion, testing for early efficacy or futility, using z-score boundaries that follow Hwang-Shih-DeCani alpha and beta spending rules (Z-value boundaries are shown in the table below).^{1,2} Following those rules, we have 84% power using 100% of the sample, if our infection rate in placebo compared to hydroxychloroquine is 10% versus 1% scenario is true. Under those circumstances, we have a 6% chance of stopping for early efficacy at the first interim analysis. Under normal circumstances (10% vs 1%), we have a 27% chance of stopping for early efficacy at the second interim analysis. We also have an 80% chance of stopping early for efficacy at the second interim analysis if the low dose arm really has 23% infection instead of 10%. Results of the interim analysis will be presented to the Data Safety and Monitoring Board (DSMB) by the study team. The DSMB will provide a recommendation of continuing or terminating the study early.

Z-Value Boundaries			
	Boundaries		Information
Stage	Efficacy	Futility	Proportion
1	2.9473	-1.2318	0.2500
2	2.5825	-0.2676	0.5000
3	1.6664	1.6664	1.0000

P-Value Boundaries			
	Boundaries		Information
Stage	Efficacy	Futility	Proportion
1	0.00160	0.89099	0.2500
2	0.00491	0.60550	0.5000
3	0.04782	0.04782	1.0000

References

- 1- Hwang, I. K., Shih, W. J., and De Cani, J. S. (1990). Group sequential designs using a family of Type I error probability spending functions. *Statistics in Medicine* 9, 1439– 45.
- 2- Jennison, C. and Turnbull, B. W. (2000). *Group Sequential Methods with Applications to Clinical Trials*. Chapman and Hall/CRC, Boca Raton, FL.

Final analyses

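### The Sub-Study 3 primary z on the log odds ratio has no named version and no zero-cell rule, and the stated stopping chances do not describe it

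*SAP*

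**What the plan says.** The SAP's Primary Analysis section states: "The primary analysis will consist of a z-test, corresponding to the log of the odds-ratio for the proportion well in the HCQ group". It adds: "The estimate will be made using either logistic regression or directly using contingency table methods". The sample-size section of the SAP describes a one-sided test "with a z-score corresponds to the log of the odds-ratio for remaining uninfected between the two groups", and Protocol 13.1 (Sub-Study 3) has the parallel wording "with a z-score corresponds to the log of the odds-ratio for recovery between the two groups".

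The sample-size sentences describe the test differently, as a z-test of two rates. The SAP has it "comparing the rates in the two groups would have 84% power to detect a significant difference". Protocol 13.1 has it "comparing the rates in the two groups would have an 80% power to detect a significant difference", and its interim paragraph for the same design gives 84%.

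For 10% v 1% the SAP's Interim Analysis section says "we have a 6% chance of stopping for early efficacy at the first interim analysis" and "we have a 27% chance of stopping for early efficacy at the second interim analysis". Protocol 13.1 also gives 81% at the first look if the control rate is 45%. Both documents give 80% at the second look if it is 23%.

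No section names Wald, score, likelihood-ratio or exact for the primary test, and none covers a zero cell. In the SAP, Fisher's exact test is named only for baseline comparisons (General section).

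**The concern.** A z on the log odds ratio is not one statistic. With large counts the versions agree, but this design expects about 10 infections against 1 at full enrolment, and 2.5 against 0.25 at the first look. With such counts the versions can fall on opposite sides of the same boundary, and the usual default, the Wald z from a logistic fit, fails when the HCQ arm has no infections. An effective drug makes that outcome likely.

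Two things are at stake. The efficacy verdict is not fully fixed in advance, because the version could be settled after the tables are seen. And the stopping chances in the plan may not be those of the test that is run.

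**Working it through.** **Inputs.** Placebo 10%, HCQ 1%, 100 per arm (SAP, sample size). Looks at 25% and 50%, taken as 25 and 50 per arm. Efficacy boundaries z = 2.9473, 2.5825, 1.6664, or one-sided p = 0.00160, 0.00491, 0.04782 (SAP, Interim Analysis). Futility is non-binding. The three z boundaries give a total one-sided alpha of 0.0500, so they are not in question.

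**1. Reproducing the plan's figures.** Pooled two-proportion approximation: Phi[(d - z x SE0)/SE1], with SE0 = sqrt(2 p(1-p)/n), p the mean rate, and SE1 = sqrt([p1(1-p1) + p2(1-p2)]/n).
- Look 1: SE0 = sqrt(2 x 0.055 x 0.945/25) = 0.0645; SE1 = sqrt(0.0999/25) = 0.0632; (0.09 - 2.9473 x 0.0645)/0.0632 = -1.58, giving 5.7% (stated 6%).
- Look 2: SE0 = 0.0456, SE1 = 0.0447; (0.09 - 2.5825 x 0.0456)/0.0447 = -0.62, giving 26.7% (stated 27%).
- Look 1 at 45% v 1%: 81.0% (stated 81%). Look 2 at 23% v 1%: 80.3% (stated 80%).
- Final look at 10% v 1%: 87.4%, which is not the stated 84%.

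**2. The same kind of approximation for the log-OR Wald z.** log OR = ln[(0.10/0.90)/(0.01/0.99)] = ln 11 = 2.398.
- Look 1: SE = sqrt(1/(25 x 0.09) + 1/(25 x 0.0099)) = 2.118; Phi(2.398/2.118 - 2.9473) = Phi(-1.815) = 3.5%.
- Look 2: SE = 1.497; Phi(1.601 - 2.5825) = 16.3%.
- 45% case: 21.1%. 23% case: 39.6%.

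So 6/27/81/80% becomes 3.5/16.3/21.1/39.6%.

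**3. Zero cells.** P(no HCQ infections) = 0.99^25 = 0.778, 0.99^50 = 0.605, 0.99^100 = 0.366. If such tables cannot reject, power cannot exceed 1 - 0.366 = 63.4%. Exact enumeration gives 54%.

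**4. Exact binomial enumeration at the printed boundaries.** The second column is the number of placebo infections needed with zero on HCQ, at looks 1/2/3. The next three columns are for 10% v 1%.

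| Version | Placebo infections needed | Stop at look 1 | Stop by look 2 | Overall power | Look 1, 45% v 1% | By look 2, 23% v 1% |
|---|---|---|---|---|---|---|
| Likelihood-ratio | 6/5/2 | 2.6% | 38% | 94% | 96% | 94% |
| Pooled score | 8/7/3 | 0.2% | 15.8% | 92.6% | 89% | 89% |
| One-sided Fisher | 9/8/5 | 0.04% | 8.2% | 84.8% | 80% | 82% |
| Log-OR with 0.5 added | 16/15/6 | 0.0% | 0.1% | 86% | 10% | 27% |
| Stated | - | 6% | 27% | 84% | 81% | 80% |

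The stated 27% reproduces as the chance of crossing at look 2 whatever happened at look 1. For the score test that chance is 15.7%, so the comparison hardly changes.

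At 25 per arm an exact 6% is not attainable by any rule monotone in the counts. If 5 v 0 rejects, the chance is at least P(5 or more placebo) x 0.778 = 7.6%. If it does not, at least 6 placebo infections are needed, and the chance is at most 3.3%.

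**5. How often the verdict differs at the final look (10% v 1%, that look's table alone).** The four usable versions are not unanimous with probability 10.5%: 2.1 points with zero HCQ infections and 8.4 points with one or more. Score and Fisher alone differ with probability 7.8%.

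**6. Type I error.** Score: 4.8% at a common rate of 3.8%, 5.0% at 10%, 5.3% at 45%, maximum 5.4% at 50%. Fisher: 2.8% at 10%, 3.9% at 45%. Likelihood-ratio: 6.6% at 3.8%, 5.5% at 10%.

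**The case against.** The other side has several good points.

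- The 6/27/81/80% are ordinary planning approximations in a design the SAP likens to phase II. They are never called exact, and no stopping decision uses them. This stands: a reader might infer an arithmetic error, but the figures reproduce. The complaint is only that they describe neither a log-OR Wald z nor the exact behaviour of any version checked.
- The pooled z for two rates is the score test of log OR = 1 on the log scale of zero, that is, of no treatment effect in the same logistic model. Describing the test by rates in one place and by the odds ratio in another is therefore not in itself a contradiction. This also stands.
- The SAP's choice between logistic regression and table methods concerns the estimate. For a two-arm table without covariates both give the same log odds ratio and Wald standard error, so that sentence is weak evidence of an open choice. The gap rests on the absence of a named version.
- A reader might infer that a zero-cell rule would suffice. It would not: 8.4 of the 10.5 points of final-look disagreement occur with at least one HCQ infection.
- Comparing score with the 0.5-corrected z gives much larger disagreement (79% at look 1 with 45% v 1%, 62% at look 2 with 23% v 1%, 16% at look 2 with 10% v 1%). Those figures depend on a correction the documents never mention, so the conclusion does not rest on them.
- The SAP uses 84% throughout, so the 80% is left only in the protocol. True, but the current protocol still carries both.
- Protocol 13.1's conditional-power rule would also be affected, but it only commits to considering a larger sample and does not give the drift. That is a secondary matter.

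**Conclusion.** The concern holds and should be fixed. The primary z is not fully specified. The default Wald version fails in an outcome with 37% probability at the final look under the plan's alternative. The usable versions reach different final verdicts in about one trial in ten at 10% v 1%, or 7.8% between score and Fisher. The stated stopping chances at 10% v 1% are well above the exact score or Fisher values.

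A reader might infer that the trial is underpowered, that the boundaries are wrong, or that a version was chosen to suit the data. The documents support none of these. The usable versions have 85% to 94% power, the printed boundaries spend 5%, and nothing shows which version was used.

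The results assume equal splits (25, 50 and 100 evaluable per arm), independent binomial counts and non-binding futility. That the stated chances came from the pooled formula is inferred from the match on all four, because the documents give no formula.

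**What to change.** Name one primary statistic for all three looks:

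- **Pooled score z** with the printed z boundaries, positive when infections are fewer on HCQ, and z = 0 if neither arm has an infection; or
- **One-sided Fisher** with the printed p boundaries.

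Do not pair the likelihood-ratio z with these boundaries, given its 6.6% type I error at the plan's cited 3.8% rate.

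Replace the stated power and stopping chances with the exact row for the chosen test from the table above, and remove the 80%/84% conflict from Protocol 13.1. Report the odds ratio with a profile-likelihood, Firth or exact confidence interval, so that a zero cell can be handled.

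The protocol supplement says Sub-Study 3 outcomes are being reported, so looks may already have been taken. If so, state which version was used and show score and Fisher results side by side.

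The cost is a few lines of text and a short calculation, with no added participants. The early-stopping chances at 10% v 1% become less favourable: with score, 6% becomes 0.2% and 27% becomes 15.8%. The score test's type I error, 5.3% at 45% and 5.4% at 50%, must be disclosed. Fisher avoids that excess but has 84.8% power instead of 92.6%.

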2.4. Clarification of language around mobile telemetry on SS1

2.5. New participant facing materials to facilitate study operations and re-consent from Amendment 1

Amendment 3 IRB approval date May 24, 2020

- 3.1 SS1 mobile telemetry clarification
- 3.2 SS1 Change from 7 to 10 days quarantine release per CDC guidelines
- 3.3 SS1 statistical analysis plan changed to specify how this will be analyzed
- 3.4 HCQ dose reduction limited to one dose level
- 3.5 Added Sandoz required language for reporting misuse of drug
- 3.6 Clarification of symptom scoring table for SS1

Amendment 4 IRB approval date: June 23, 2020

- 4.1 establishment of a Data Safety and Monitoring Board (slide 29)
- 4.2 SS3 Secondary objective # shifts missed removed as this measurement is not useful
- 4.3 Removed some Sub-Is.
- 4.4 Clarification of evaluable patients section 10 excludes SS3 PCR+ subjects at baseline from primary outcome.
- 4.5 clarification that subjects that withdraw from treatment can complete other study procedures.
- 4.6 clarification that subjects must agree to self report pregnancy during study and 90 days post. This is in accordance with the current consent form.

**The PATCH (Prevention And Treatment of COVID-19 with HCQ) Trial:
A 2 Arm Randomized Trial of Hydroxychloroquine in the Prevention and Treatment of COVID-19**

Sponsor-Investigator/ Principal Investigator:	[name] (Medicine) University of Pennsylvania Perelman School of Medicine Department of Medicine, Division of Hematology Oncology [name] [contact]
Primary Emergency Medicine Sub-Investigator	[name] (Emergency Medicine) University of Pennsylvania Perelman School of Medicine Department of Emergency Medicine Hospital of the University of Pennsylvania Emergency Department, [name] [contact]
Primary Infectious Diseases Sub-Investigator	[name] [name] [contact]
Other Significant Sub-Investigators	[name] (EM) [name] (EM) [name] (EM) [name] (EM) [name] (EM) [name] PhD (Pathology) [name] (ID) [name] (Statistics) [name] (Statistics) [name] (Cardiology) [name], PhD (Cardiology) [name] (Oncology) [name] (Oncology) [name] Md PhD (Oncology) [name] (Oncology) [name] (Oncology)
Medical Monitor:	[name] University of Pennsylvania Perelman School of Medicine Department of Medicine, Division of Hematology Oncology [contact] [contact]

PATCH 1 Trial

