10.0 MEASUREMENT OF EFFECT

10.1 Definitions

Evaluable for toxicity. All participants will be evaluable for toxicity from the time of their first treatment with HCQ or placebo.

Evaluable for primary outcome: Participants who received at least one dose of study drug will be evaluable for the primary outcome as long as they meet the following status for SARS-COV2 PCR: sub-study 1: PCR+ Sub-study 3: PCR negative.

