10.3 Off treatment/Off Study

Each participant has the right to withdraw from the study at any time without prejudice. The investigator may discontinue any person's participation for any reason, including adverse event or failure to comply with the protocol. Should a participant withdraw from the study, the reason(s) must be stated on the case report form, and a final evaluation of the participant should be performed. Reasons for withdrawal include the following:

Progression of Disease: Remove participant from protocol therapy at the time progressive disease is documented. Progression of disease is left to the discretion of the treating physician/ sub-Investigator; however, the following guidelines are provided to help decision making for discontinuing study drug:

Sub-study 1: Progression of disease can be confirmed if there is increase in COVID-19 symptom score for 2 days in a row and is three points higher than baseline. Once criteria for release from quarantine is met in SS1 the patient is off study. Once the person is hospitalized for COVID-19 in sub-study 1 the subject is off study. Participants who have progressive symptoms and are subsequently hospitalized as related to COVID-19 will not be crossed over to receive HCQ at the time of unblinding.

Sub-study 3: Development of new symptomology consistent with COVID-19: e.g. fever, cough, shortness of breath and SARS-COV2 test positivity would lead to unblinding. If on placebo the subject can crossover to HCQ for treatment and stay on study for 14 days or release from quarantine. If the subject was on HCQ the subject is off study and will be instructed to seek medical attention through their primary care physician

Extraordinary Medical Circumstance: If at any time the treating physician feels constraints of this protocol are detrimental to the participant's health remove the participant from protocol therapy.

Participant's refusal to continue treatment: In this event, document the reason(s) for withdrawal.

Failure to comply with protocol (as judged by the investigator such as compliance below 80%, failure to maintain appointments, etc.).

Withdrawal from treatment per patient choice: Patients may withdraw from study treatment at any point in the study for any reason. These subjects are allowed to withdraw from treatment but continue to participate with any of the other study procedures for the intended 2 month period.

Delay in treatment > 7 days due to toxicity

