Upon completion of the trial and the necessary data cleaning, the dataset will be locked for final analysis. This may occur at the final sample size of N=200, or earlier in the case of a decision to halt for futility. This final analysis will be conducted by study staff under supervision of the PIs with full involvement of two study statisticians. PIs and statisticians will review all results and p-values before analysis is determined complete and before manuscript submission.

Analysis Set	Definition	Outcomes
Randomized patients	Any patient randomized	Demographics
Evaluable for primary outcome	Randomized covid-19 negative at baseline and took at least one dose of study drug, and either completed all study procedures or	Primary outcome
Evaluable for Safety	Randomized and took one dose of study drug	Adverse events
Evaluable for drug-induced QTc prolongation	Randomized COVID-19 negative at baseline, took at least one dose of study medication and had a baseline and one month EKG	Change in QTc
Evaluable for antibody prevalence	Subjects who had blood drawn at specified timepoint	Antibody prevalence

Missing Data

Missing data values will not be imputed. Only observed values will be used for data analysis and presentation.

Subject Disposition

The summary statistics of the subjects will include the following information:

- The number and percentage of subjects who complete the trial and who drop out before trial completion according to the treatment groups.
- The number and percentage of subjects per analysis population according to the treatment groups.

Protocol Deviations

All protocol violations will be listed. The sponsor and/or its designee will review the protocol violations before the database is locked, and determine whether the involved subjects will be excluded from the per protocol set.

Demographic and Baseline Variables

The following demographic and baseline variables collected prior to the start of study medication will be summarized by treatment group.

Sex

Age

Profession (MD, nurse, respiratory technician, etc)

Location of work (ICU, ward, emergency department, etc)

Past medical history

Baseline testing will include NP swab testing for SARS-CoV-2, serologic testing for antibodies against SARS-CoV-2, and ECG testing (protocol amended DATE to include as a baseline test).

Adverse event reporting

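### Does the SAP's primary analysis set narrow the protocol's by requiring that all study procedures be completed?

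*SAP*

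**What the plan says.** Protocol 10.1 sets two conditions for the sub-study 3 primary outcome, treatment and PCR status: "Participants who received at least one dose of study drug will be evaluable for the primary outcome as long as they meet the following status", which for this sub-study is PCR negative. It says nothing about completing follow-up.

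The SAP, in the Analysis Set table under Final analyses, requires a negative baseline test and that the participant "took at least one dose of study drug, and either completed all study procedures or" met some second alternative. The cell stops there in the available copy. Lost text is not a fault in the plan.

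Neither change record mentions completion. Item 4.4 of the protocol's Amendment 4 summary reads "Clarification of evaluable patients section 10 excludes SS3 PCR+ subjects at baseline from primary outcome". The SAP's own amendment table adds "Evaluable patients for primary outcome finalized".

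Three other provisions bear on the point:

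- The SAP's Missing Data paragraph rules out imputation and uses observed values only.
- The SAP's primary objective counts an infection found by the study swabs at weeks 4 and 8, or by a confirmed clinical test before week 8.
- Protocol 10.3 treats infected participants differently by arm. For HCQ, "If the subject was on HCQ the subject is off study and will be instructed to seek medical attention". For placebo, "If on placebo the subject can crossover to HCQ for treatment and stay on study for 14 days or release from quarantine".

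**The concern.** Joined to the other conditions by *and*, the completion clause makes membership of the primary set depend on events after randomisation. If completion differed by arm, the comparison would no longer be protected by randomisation. The single primary test would also have two candidate populations, one in each document.

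Protocol 10.3 sharpens the worry. An infected HCQ participant goes off study and so cannot finish the schedule, while an infected placebo participant may stay. If such HCQ infections were lost from the set, HCQ would look better than it is. Separately, a participant who stops treatment is "allowed to withdraw from treatment but continue to participate with any of the other study procedures", so partial completion among uninfected people is to be expected, and the SAP does not define which procedures must be complete.

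**Working it through.** No figure in the plan is disputed, so the check is to ask who could be in one set and not in the other. Take dosed participants with a negative baseline PCR.

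1. **Finished everything.** In both sets.
2. **PCR positive by week 8, schedule not finished.** In the protocol's set. Protocol 8.4.2 counts a positive one-month or two-month swab as a primary event, and the SAP objective counts a clinical positive before week 8. The SAP sentence offers an alternative to completion, and an early positive is the one way the endpoint becomes known without finishing. A second alternative that left these people out would contradict both passages.
3. **No positive and no week-8 result.** Nominally in the protocol's set. The SAP's Primary Analysis compares the proportions well at the end of 8 weeks, so on its natural reading these people have no observed outcome. The observed-values rule removes them under either definition.
4. **Known negative through week 8, some other procedure missed.** In the protocol's set. In the SAP's set if the clause means finishing PCR follow-up; out if it means every scheduled item and the second alternative admits only infections.

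Only group 4 is really in question. Two things favour the milder meaning. The QTc set states its own ECG requirement ("took at least one dose of study medication and had a baseline and one month EKG") and the antibody set its own blood requirement, so those procedures are handled where they matter. The notes to the protocol's Table 6 let ECGs and research blood be deferred, so a literal reading would exclude people for something the protocol allows.

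Now suppose the literal reading anyway. Let placebo have *a* infected and *b* negative, and HCQ *c* infected and *d* negative. The odds ratio of infection, HCQ v placebo, is

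OR = (c/d) / (a/b).

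If shares r_P and r_H of the known negatives are kept,

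OR′ = (c/(r_H·d)) / (a/(r_P·b)) = OR × r_P/r_H.

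Equal shares leave it unchanged. Fewer negatives kept on HCQ moves the result against HCQ; fewer kept on placebo moves it in favour.

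A borderline table shows the scale: 100 per arm (SAP sample size), 10 placebo and 4 HCQ infections (assumed), final efficacy boundary 1.6664 (SAP). The z is the log odds ratio, placebo v HCQ, over its standard error.

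- Everyone kept: ln[(10/90)/(4/96)] = 0.981; SE = √(1/10 + 1/90 + 1/4 + 1/96) = 0.610; z = 1.609.
- Four placebo negatives left out: ln[(10/86)/(4/96)] = 1.026; SE = √(1/10 + 1/86 + 1/4 + 1/96) = 0.610; z = 1.683, across the boundary.
- Four left out of each arm: ln[(10/86)/(4/92)] = 0.984; SE = √(1/10 + 1/86 + 1/4 + 1/92) = 0.610; z = 1.612, not across.

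It is the imbalance, not the exclusion, that matters. For the uninfected, neither document gives a completion figure or a rule that differs by arm. The rule on withdrawal from treatment in protocol 10.3 is the same for both, and treatment is blinded. The arm difference in 10.3 concerns infected people, who belong to group 2.

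**The case for a change.** The strongest case is that the two texts plainly differ. If the missing alternative admitted everyone with a known PCR outcome, the completion clause would be almost redundant, so the harmless reading is not the obvious one. A second alternative covering infections alone would count every known positive but only those negatives who finished everything.

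Under that reading, with 100 per arm, a true 10% in both arms and interim looks ignored, the one-sided rejection rate (pooled z) is 4.9% with nobody left out. It is 2.8% if 90% of placebo and 80% of HCQ negatives are kept, and 8.0% if those shares are reversed. If instead one in ten HCQ infections were lost, it would be 7.2%. Aligning the wording would cost almost nothing.

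The arithmetic is sound, and the texts do differ in their legible words. What does not stand is the step to a defect in this plan. The unequal shares are assumed. With 90% kept in both arms the rate stays at 4.9%. The loss of HCQ infections runs against two passages that count them as events. Side effects might reduce completion more on HCQ, but no completion figure is given, and that imbalance would work against HCQ. Finally, the SAP commits to reporting the number in each analysis population by arm, so any exclusions would be visible, although reporting them would not correct for them.

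**Conclusion.** No change is needed. The legible wording leaves a definition incomplete; it does not show that following the plan would give a wrong or worse primary result. An analyst who reads the clause with the SAP's endpoint and its observed-values rule would analyse everyone whose PCR outcome is known, which gives the same data as protocol 10.1.

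This rests on two readings that the available text supports but cannot prove: that the second alternative admits participants who tested positive, and that completion refers to PCR follow-up. If the second fails, the effect is still nil on the odds ratio when equal shares of known negatives are kept in each arm, and otherwise unknown in size and direction. Confirming the full cell with the sponsor is ordinary housekeeping before the database is locked.
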